6.7. Intervention after the End of the Study

6.7.1. Treatment after Study Completion

Tirzepatide will not be made available to participants after conclusion of the study.

7. Discontinuation of Study Intervention and Participant Discontinuation/Withdrawal

7.1. Discontinuation of Study Intervention

Possible reasons leading to permanent discontinuation of IP:

- **participant decision**
 - the participant requests to discontinue IP.
- **clinical considerations**
 - initiation of open-label GLP-1R agonist or DPP-4 inhibitor, if participants will not or cannot discontinue them
 - intolerable GI symptoms despite management as described in Section 6.6.2
 - BMI ≤ 18.5 kg/m² is reached at any time during the treatment period
 - Note:* The investigator should contact the Sponsor CRP to discuss whether it is medically appropriate for the participant to continue study treatment.
 - diagnosis of T1DM
 - diagnosis of MTC after randomization
 - significant elevation of calcitonin (Section 10.3.1.4)
 - diagnosis of acute or chronic pancreatitis
 - diagnosis of an active or untreated malignancy (other than basal or squamous cell skin cancer, in situ carcinomas of the cervix, or in situ prostate cancer) after randomization
 - development of any significant study drug-related hypersensitivity reaction
 - onset of pregnancy in a female participant
 - occurrence of any other treatment-emergent AE (TEAE), SAE, or clinically significant finding for which the investigator believes that permanent study drug discontinuation is the appropriate measure to be taken
 - inadvertent enrollment if continued treatment with study drug would not be medically appropriate (Section 7.2.3)
 - PHQ-9 score ≥ 15

- Participants should be referred to a Mental Health Professional (MHP) to assist in deciding whether the subject should be discontinued from study drug. If a participant's psychiatric disorder can be adequately treated with psycho- and/or pharmacotherapy, then the subject, at the discretion of the Investigator (in agreement with the MHP), may be continued in the trial on randomized therapy.
- in addition, study drug may be discontinued if participants:
 - answered "yes" to either Question 4 (Active Suicidal Ideation with Some Intent to Act, Without Specific Plan) on the "Suicidal Ideation" portion of the C-SSRS
 - or**
 - answered "yes" to Question 5 (Active Suicidal Ideation with Specific Plan and Intent) on the "Suicidal Ideation" portion of the C-SSRS
 - or**
 - answered "yes" to any of the suicide-related behaviors (Actual attempt, Interrupted attempt, Aborted attempt, Preparatory act or behavior) on the "Suicidal Behavior" portion of the C-SSRS.

Note: A psychiatrist or appropriately trained professional may assist in the decision to discontinue the participant.

- **discontinuation due to a hepatic event or liver test abnormality**

- Participants who are discontinued from IP due to a hepatic event or liver test abnormality should have additional hepatic safety data collected via eCRF.
- Discontinuation of the IP for abnormal liver tests **should be** considered by the investigator when a participant meets one of the following conditions after consultation with the Lilly designated medical monitor:
 - ALT or aspartate aminotransferase (AST) >8X ULN
 - ALT >2X baseline value OR ≥ 300 U/L, whichever occurs first, if baseline ALT ≥ 2 X ULN
 - ALT or AST >5X ULN for more than 2 weeks
 - ALT or AST >3X ULN and total bilirubin level (TBL) >2X ULN or international normalized ratio (INR) >1.5
 - ALT or AST >3X ULN with the appearance of fatigue, nausea, vomiting, right upper-quadrant pain or tenderness, fever, rash, and/or eosinophilia (>5%)
 - alkaline phosphatase (ALP) >3X ULN
 - ALP >2.5X ULN and TBL >2X ULN

- ALP >2.5X ULN with the appearance of fatigue, nausea, vomiting, right-quadrant pain or tenderness, fever, rash, and/or eosinophilia (>5%)

Participants who stop study drug permanently should continue to attend all scheduled study visits to collect all planned efficacy and safety measurements. Participants who are unwilling to attend all scheduled visits and stop the study prior to 72 weeks, should return for a final weight measurement (Visit 99). If participants are unwilling to attend Visit 99, their refusal to attend should be documented in the patient medical record. Participants with prediabetes who stop study drug after 72 weeks should return for a final assessment of weight and glycemic status (Visit 199). Refusal to attend should be documented in the patient medical record.

Participants discontinuing from the IP prematurely for any reason should complete AE and other follow-up procedures per Section 1.3 (Schedule of Activities), Section 8.3 (Adverse Events and Serious Adverse Events), and Section 8.2 (Safety Assessments) of the protocol.

7.1.1. Temporary Study Drug Discontinuation

In certain situations, after randomization, the investigator may need to temporarily interrupt study drug. Every effort should be made by the investigator to maintain participants on study drug and to restart study drug after any temporary interruption, as soon as it is safe to do so. Distribution of study medication at the correct dose will be per IWRS instructions.

If study drug interruption is...	then...
2 consecutive doses or less	participant restarts study drug at last administered dose, as per escalation schedule.
3 consecutive doses or more	participant restarts study drug (at 5 mg, managed by IWRS) and repeats dose escalation scheme.
due to an AE	the event is to be documented and followed according to the procedures in Section 8.3 of this protocol.
due to intolerable persistent GI AE	participants should be treated as suggested in Section 6.6.2.

Abbreviations: AE = adverse event; GI = gastrointestinal; IWRS = interactive web response service.

Investigators should inform Lilly that study drug has been temporarily interrupted. The data related to temporary interruption of study treatment will be documented in source documents and entered on the eCRF.

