Visit 99 Visit 199	Participants wanting to discontinue the study before Week 72 will be asked to return for Visit 99 at 72 weeks \pm 7 days after randomization primarily for body weight measurement and assessment of adverse events. If the participant is unwilling to attend Visit 99, it should be documented in the participant medical record that the participant has refused to attend. Participants wanting to discontinue the study after Week 72 but before Week 176 will be asked to return for Visit 199 primarily for the body weight measurement and assessment of adverse events. Refusal to attend should be documented.

ED	Participants who are unable or unwilling to continue the study treatment for any reason will perform an ED visit. If the participant is discontinuing during an unscheduled visit or a scheduled visit, that visit should be performed as the ED visit.
Safety Follow-up Visits Visit 801 Visit 802	For participants who discontinue or complete the study within the first 72 weeks, Visit 801 (safety follow-up visit) should be performed 4 weeks after the last visit during the 72-week treatment period. Participants with prediabetes continuing to Week 78 should not perform Visit 801. For participants with prediabetes who complete the 176 weeks or discontinue after Week 72, Visit 802 should be performed 17 weeks after the last visit during the additional 2-year treatment period for participants with prediabetes at randomization.
Allowable Deviation (days)	The visit date is determined in relation to the date of the randomization visit (\pm the allowed visit window).
Medical History	Medical history includes assessment of preexisting conditions (for example, history of gallbladder disease, cardiovascular disease, and medullary thyroid carcinoma) and substance usage (such as alcohol and tobacco).
Weight	Weight measurements should be obtained per the instructions in Section 10.7. Body weight must be measured in fasting state. If the participant is not fasting, the participant should be called in for a new visit within the visit window to have the fasting body weight measured.
Electrocardiogram	ECG measurements should be obtained per the instructions in Section 10.7. ECGs will be performed in triplicate at Weeks 0 and 36. All other ECGs will be single measurements. ECGs should be collected at least 30 minutes prior to collection of blood samples for laboratory testing, including PK samples.

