- review of participant diary information (to include reinforcement and compliance assessments for study drug administration and lifestyle goals)
- administration of questionnaires
- laboratory testing
- drug dispensing
- collect AEs, product complaints and concomitant medications

Mental Health Questionnaires should be completed after the assessment of AEs.

Dietician consultations continue at Weeks 4, 8, 12, and then every 12 weeks thereafter, to Week 72. Study drug and injection supplies will be returned per the Schedule of Activities (Section 1.3) and according to local requirements. New supplies will be dispensed as needed.

Study drug dose escalation is double-blinded and will be managed via the interactive web-response system (IWRS). The starting dose is 2.5 mg QW (or matching placebo) for 4 weeks, then the dose is increased by 2.5 mg (or matching placebo) every 4 weeks: 2.5 to 5 mg for those randomized to 5 mg, 2.5 to 5 to 7.5 to 10 mg for those randomized to 10 mg, and continuing to 12.5 to 15 mg for those randomized to 15 mg. The dose is then maintained up to 72 weeks.

At each of the 8 scheduled telephone visits, procedures will include:

- reinforcement and compliance assessments for study drug administration and lifestyle goals,
- listing of concomitant medications
- AE and Product Complaints (PCs) assessment (see Schedule of Activities Section 1.3.1)
- administration of questionnaires

Participants should be instructed to contact the investigative site for assistance as soon as possible if they experience any difficulties administering their study medication. Participants should also be advised about the appropriate course of action in the event that study drug is not taken at the required time (late/missing doses).

Study participants will be permitted to use concomitant medications that they require during the study, except certain excluded medications (see Section 5.2) that may interfere with the assessment of efficacy and safety characteristics of the study treatments.

For those participants without glycemic evidence of T2DM (Section 4.1.2.1), a 2-hour oral OGTT will be performed at Visit 21.

Visit 99

Visit 99 is only applicable to participants who discontinue the study treatment prematurely (before Week 72). Participants will be asked to return for Visit 99 at 72 weeks \pm 7 days after

randomization. This visit is critical to ensure complete data collection for the primary weight-loss endpoint.

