4.3. Justification for Dose

Tirzepatide doses of 5 mg, 10 mg, and 15 mg QW will be evaluated in this study. These doses and associated escalation schemes were selected based on assessment of safety, efficacy (weight loss), and GI tolerability data, followed by exposure-response modeling of data in patients in Phase 1 and 2 studies that predicted weight loss in obese and overweight patients without T2DM.

Dosing algorithms starting at a low dose of 2.5 mg accompanied by dose escalation of 2.5-mg increments every 4 weeks should permit time for development of tolerance to GI events and are predicted to minimize GI tolerability concerns. The maximum proposed dose of 15 mg maintains an exposure multiple of 1.6 to 2.4 to the no-observed adverse-effect level doses in 6-month monkey and rat toxicology studies.

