5.1. Inclusion Criteria

Participants are eligible to be included in the study only if all of the following criteria apply:

Type of Participant and Disease Characteristics

1. Have a BMI
 - ≥ 30 kg/m² or
 - ≥ 27 kg/m² and previously diagnosed with at least one of the following weight related comorbidities:
 - hypertension: treated or with systolic blood pressure (SBP) ≥ 130 mmHg or diastolic blood pressure ≥ 80 mmHg
 - dyslipidemia: treated or with low-density lipoprotein (LDL) ≥ 160 mg/dL (4.1 mmol/L) or triglycerides ≥ 150 mg/dL (1.7 mmol/L), or high-density lipoprotein (HDL) < 40 mg/dL (1.0 mmol/L) for men or HDL < 50 mg/dL (1.3 mmol/L) for women
 - obstructive sleep apnea
 - cardiovascular disease (for example, ischemic cardiovascular disease, New York Heart Association (NYHA) Functional Class I-III heart failure)
2. Have a history of at least one self-reported unsuccessful dietary effort to lose body weight
3. In the investigator's opinion, are well-motivated, capable, and willing to
 - learn how to self-inject study drug, as required for this protocol (visually impaired persons who are not able to perform the injections must have the assistance of a sighted individual trained to inject study drug; persons with physical limitations who are not able to perform the injections must have the assistance of an individual trained to inject study drug)
 - inject study drug (or receive an injection from a trained individual if visually impaired or with physical limitations)
 - follow study procedures for the duration of the study, including, but not limited to: follow lifestyle advice (for example, dietary restrictions and exercise plan), maintain a study diary, and complete required questionnaires

Participant Characteristics

4. Are 18 years or older

a. male participants:

- Male participants with partners of childbearing potential should be willing to use reliable contraceptive methods throughout the study and for 5 half-lives of study drug plus 90 days, corresponding to 4 months after the last injection.

b. female participants:

- Female participants not of childbearing potential may participate and include those who are:
 - infertile due to surgical sterilization (hysterectomy, bilateral oophorectomy or tubal ligation), congenital anomaly such as Mullerian agenesis
 - postmenopausal, defined as either

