6.6.2. Management of Participants with Gastrointestinal Symptoms

Participants who experience intolerable GI symptoms (for example, nausea, vomiting, or diarrhea) at any time during the study, should first be counselled on dietary behaviors that may help mitigate nausea and vomiting, (for example, eating smaller meals, splitting 3 daily meals into 4 or more smaller ones, and stopping eating when they feel full). If symptoms persist, the participant should be prescribed, at the investigator's discretion, symptomatic medication (for example, antiemetic or antidiarrheal medication). A temporary interruption of study drug for 1 dose is permitted, provided the participant has taken the last 3 weekly doses. Study treatment should be resumed at the assigned dose immediately, either alone or in combination with symptomatic medication, which can also be utilized to manage symptoms (Section 10.9). Management of study drug after interruptions >1 dose is discussed in Section 7.1.1.

If intolerable GI symptoms (for example, nausea, vomiting, or diarrhea) persist despite the above measures, the investigator should contact Lilly to consider reinitiating study drug at the next-lowest maintenance dose in a blinded fashion (for example, 15 mg reduced to 10 mg, 10 mg reduced to 5 mg, or 5 mg reduced to placebo) (Section 10.9).

If intolerable GI symptoms persist despite symptomatic treatment, temporary drug interruption, and resumption at a lower dose of study drug, the participant should be discontinued from study drug. All participants who discontinue study drug should continue to attend scheduled study visits.

6.6.3. Management of Participants with Perceived Excessive Weight Loss During the Additional 2-year Treatment Period for Participants with Prediabetes at Randomization

As indicated in Section 5.3.1, if BMI ≤ 22 kg/m² is reached any time during the study, the recommended energy intake should be recalculated. From Visit 101 onwards, in the participants who have reached BMI ≤ 22 kg/m², if weight loss continues despite above measures and/or there are concerns related to degree of weight loss that may lead to discontinuation from study drug, the investigator should contact the Sponsor CRP to consider a study drug dose reduction in a blinded fashion (see Section 6.6.2 for details regarding study drug dose reduction).

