8.2.4.1. Immunogenicity Assessment

Where local regulations and ERBs allow, blood samples for immunogenicity testing will be collected to determine antibody production against tirzepatide as specified in the Schedule of Activities (Section 1.3).

At the visits and times specified in the Schedule of Activities (Section 1.3), venous blood samples will be collected to determine antibody production against tirzepatide. To interpret the results of immunogenicity, a PK sample will be collected at the same time points as the immunogenicity sample. All samples for immunogenicity should be taken predose when applicable and possible. In the event of systemic drug-hypersensitivity reactions (immediate or nonimmediate), additional samples will be collected (including antidrug antibodies [ADAs], PK, and exploratory biomarker samples) as close to the onset of the event as possible, at the resolution of the event, and 30 days following the event. Instructions for the collection and handling of blood samples will be provided by the Sponsor. The actual date and time (24-hour clock time) of each sampling will be recorded. Immunogenicity will be assessed by a validated assay designed to detect ADAs in the presence of tirzepatide at a laboratory approved by the Sponsor. Antibodies may be further characterized and/or evaluated for their ability to neutralize the activity of tirzepatide. Sample collected at Visit 801 or Visit 802 will assess immunogenicity at washout of tirzepatide (5 half-lives post end of treatment).

Samples with tirzepatide ADA detected will be titered and evaluated for their ability to neutralize the activity of assigned treatment (tirzepatide-neutralizing antibodies). Samples with tirzepatide ADA detected will also be tested for cross-reactive binding to native GIP and GLP-1, and if such is detected, then for neutralizing antibodies against native GIP and GLP-1, respectively.

Treatment-emergent ADAs are defined in Section 9.4.6.

Samples will be retained for a maximum of 15 years after the last participant visit, or for a shorter period if local regulations and ERBs allow, at a facility selected by the Sponsor. The duration allows the Sponsor to respond to future regulatory requests related to tirzepatide. Any samples remaining after 15 years will be destroyed.

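### The 5 mg restart after three or more missed doses makes no exception for a participant still in the 2.5 mg lead-in, who then meets 5 mg without completing it

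*Protocol*

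**What the plan says.** Protocol Section 7.1.1 applies to temporary interruptions at any time after randomization and has two rows keyed to length.

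- Two consecutive doses or fewer: "participant restarts study drug at last administered dose, as per escalation schedule".
- Three or more: "participant restarts study drug (at 5 mg, managed by IWRS) and repeats dose escalation scheme".

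Neither row refers to the dose step reached or the number of doses taken. Section 6.6.1 rules out other dose changes except for intolerable gastrointestinal (GI) symptoms and, in the additional two-year period, perceived excessive weight loss. Nothing written provides for a 2.5 mg restart.

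Section 4.1.1.2.2 describes the lead-in: "The starting dose is 2.5 mg QW (or matching placebo) for 4 weeks, then the dose is increased by 2.5 mg" every four weeks. Section 4.3 gives the reason: starting at 2.5 mg with "dose escalation of 2.5-mg increments every 4 weeks should permit time for development of tolerance to GI events".

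For GI symptoms, Section 6.6.2 allows a one-dose interruption and then refers on: "Management of study drug after interruptions >1 dose is discussed in Section 7.1.1". The GI row of Section 7.1.1 points back to Section 6.6.2. The SAP does not address restart dosing; its Section 6.11.2 provides only for an optional summary of dose interruptions.

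**The concern.** The lead-in exists so that nobody meets 5 mg before four weeks at 2.5 mg. The row for three or more missed doses suits someone who had already reached 5 mg or more, since 5 mg is then a step back or a repeat. For someone interrupted during the 2.5 mg step it is a step up, taken after a gap of at least four weeks and with the lead-in unfinished.

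In the 5 mg arm the only escalation is from 2.5 to 5 mg, so repeating the escalation from 5 mg means no escalation at all. If such a participant does not tolerate the restart, the one-dose pause in Section 6.6.2 requires that the last three weekly doses were taken. The listed reduction from 5 mg is to placebo, and Section 6.6.1 allows only one reduction. Early GI intolerance, and perhaps loss from study drug, is what is at stake. Participants on placebo restart on matching placebo, so the point concerns the three tirzepatide arms.

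**Working it through.** The plan states no figure to reproduce. The check is date arithmetic, followed by a test of whether residual drug adds anything.

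**1. Timing.** Dosing is weekly (Section 6.1). With k doses of 2.5 mg taken, the last dose is at Week k − 1. Three missed doses put the restart at Week k + 3, a gap of 28 days. This is the minimum, because longer gaps fall under the same row. From a 5 mg restart, 15 mg is four steps of four weeks away (restart + 16 weeks). From a 2.5 mg restart it is five steps away (restart + 20 weeks).

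| k | Weeks missed | Restart | 15 mg as written (weeks left to Week 72) | 15 mg if restarted at 2.5 mg (weeks left) |
|---|---|---|---|---|
| 1 | 1–3 | Week 4 | Week 20 (52) | Week 24 (48) |
| 2 | 2–4 | Week 5 | Week 21 (51) | Week 25 (47) |
| 3 | 3–5 | Week 6 | Week 22 (50) | Week 26 (46) |
| 4 | 4–6 | Week 7 | Week 23 (49) | Week 27 (45) |

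**2. Order of the two rows.** With one dose taken and two missed, the restart is at Week 3. Both the last dose and the schedule then give 2.5 mg. With one taken and three missed, it is 5 mg at Week 4. With two or three taken, 5 mg is already due by the calendar when dosing resumes after two missed doses, so no inversion is claimed there.

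**3. Half-life.** The documents state none, so a range has to be inferred.

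- Section 8.2.4.1 says: "Sample collected at Visit 801 or Visit 802 will assess immunogenicity at washout of tirzepatide (5 half-lives post end of treatment"). The notes to Section 1.3 say: "Visit 801 (safety follow-up visit) should be performed 4 weeks after the last visit during the 72-week treatment period". If five half-lives are 28 days, the half-life is 28 / 5 = 5.6 days.
- If the last injection was a week before that last visit, five half-lives are 35 days and the half-life is 7 days.
- Section 5.1 asks for contraception "for 5 half-lives of study drug plus 90 days, corresponding to 4 months after the last injection". Taking four months as 120 days, (120 − 90) / 5 = 6 days.

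A 28-day gap is therefore 28 / 7 = 4 to 28 / 5.6 = 5 half-lives.

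**4. Residual drug.** Assume first-order elimination and ignore absorption. Weekly retention is r = 2^(−7 / half-life). In the planned sequence, the amount left at the first 5 mg dose is 2.5 × (r + r² + r³ + r⁴). At a restart after k doses and three missed it is 2.5 × (r⁴ + … + r^(k+3)).

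| mg dose-equivalents | 5.6 days (r = 0.420) | 6 days (r = 0.445) | 7 days (r = 0.500) |
|---|---|---|---|
| Planned, Week 4 | 1.76 | 1.93 | 2.34 |
| Restart, k = 1 | 0.078 | 0.098 | 0.156 |
| Restart, k = 2 | 0.111 | 0.142 | 0.234 |
| Restart, k = 3 | 0.125 | 0.162 | 0.273 |
| Restart, k = 4 | 0.131 | 0.171 | 0.293 |

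For k = 1 to 3 this is about 4% to 12% of the planned amount. The k = 4 row matters most. A participant who completed the lead-in has almost the same residue as one who took three doses (0.131 against 0.125 mg at 5.6 days). Residual drug therefore does not mark out the group at issue; the number of 2.5 mg doses taken does.

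**The case against.** The strongest reply is that the protocol accepts a 5 mg restart after a gap of this length for everyone, including those who completed the lead-in, and that residual drug is about the same for both. That stands. A reader might infer that washout is the fault, but the documents do not support this. Besides the near-equal residues, the washout sentence covers Visit 802, at 17 weeks, as well as Visit 801, so it does not fix 28 days as five half-lives.

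A reader might also infer that affected participants reach 5 mg ahead of schedule. They do not: restart falls at Week 4, 5 or 6, and 5 mg is due from Week 4. What differs is that they have taken one to three lead-in doses, not four.

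Nor do the documents show that 5 mg is unsafe without a full lead-in. Section 2.2 gives 5 mg as the maximum tolerated single dose in the Phase 1 study, but the same study included 5 mg weekly multiple dosing in type 2 diabetes. That supports a tolerability concern and no more.

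Safeguards exist. Study drug is restarted only when safe, the sponsor is informed, IWRS controls dispensing, and Section 6.6.2 offers symptomatic care and dose reduction. The IWRS logic and the Section 10.9 flowchart are not visible and may settle GI-related gaps. But the row names 5 mg explicitly, so dispensing 2.5 mg would depart from the text, and interruptions for non-GI reasons fall under the row in any case.

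**Conclusion.** The point holds as a gap in the written restart rule. A participant interrupted for three or more doses after one to three lead-in doses is sent to 5 mg at least 28 days after the last dose, contrary to the dose rationale in Sections 4.1.1.2.2 and 4.3. The inversion between the two rows is confined to exactly one dose taken.

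The argument is the incomplete lead-in and does not depend on the inferred half-life of 5.6 to 7 days. It does assume that IWRS follows the row as written. The number affected cannot be estimated from the documents and is probably small. A reader might look for an effect on the trial's conclusions, but no endpoint, alpha or power figure depends on this. It is a minor safety and tolerability improvement.

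**What to change.** Confirm what IWRS dispenses in this case, then amend the row to read:

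> 3 consecutive doses or more: if the interruption began before the first 5-mg dose (or matching placebo), restart at 2.5 mg (or matching placebo) for 4 weeks and then continue the escalation; otherwise restart at 5 mg (or matching placebo), managed by IWRS, and repeat the escalation.

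The condition is tied to the step at which the interruption began. A count of 2.5 mg doses taken would also catch someone who skipped one lead-in dose, reached 15 mg and was interrupted much later. The wording does include a participant who took all four 2.5 mg doses but no 5 mg dose (k = 4 in the timing table: 45 weeks at 15 mg instead of 49). The sponsor should decide whether that is intended.

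The cost is one table row and an IWRS check. For k = 1 to 3 with exactly three missed doses, time at 15 mg before Week 72 falls to 46 to 48 weeks from 50 to 52, against the 52 weeks named in Section 4.2; the current row already gives 51 and 50 for k = 2 and 3. In the 10 mg arm, 54 to 56 weeks remain instead of 58 to 60, still above 52. Each further missed dose takes one more week. At the Week 20 key secondary visit an affected 15 mg participant would be one 2.5 mg step lower.
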